Study announcements will be distributed by aging and health service agencies using organizational contact lists via mail and email. In addition, study announcements will be posted at various health, human service and community-based organizations (e.g., health clinics, support groups, buddy programs, community-based churches, and social groups) and published in community-based newspapers and newsletters. Potential participants (LGBT older adults with dementia) will be asked to contact the study directly after learning about it. Callers who contacted the Aging with Pride: Innovations in Dementia Empowerment and Action (IDEA) original study and who did not have caregivers were asked if we could contact them when this study is available. We will call or email those who responded “yes” to announce this study.

Using chain referral sampling we will send an email or letter inviting participants who have completed the study to tell their friends about the study. We will ask these participants to share the flyer provided in the email or letter. We will reimburse individuals \$20 for each person that successfully enrolls in the study. We will ask those who call how they learned about the study. The caller will need to name the referring individual for us to send the referring individual \$20. Callers won’t be required to provide the name of the referring individual if they wish to keep their participation in the study confidential. If the caller doesn’t name a referring individual, the caller may still enroll in the study if eligible. Referring individuals will be paid no more than \$60 for 3 people that enroll.

- b. Recruitment materials: Study announcements will be distributed by mail and email using aging and health service agencies’ contact lists and will be posted at various health, human service and community-based organizations, and published in community-based newspapers and newsletters. Upon expressing interest in participating, initial screening of eligibility will be conducted by telephone using a script including the purpose and design of the study and a brief review of key elements of the consent form and an eligibility screen assessment form.
- c. Payment to participants: Participants will receive \$25 for each assessment they complete; there are two assessments in total: a pre-treatment and a post-treatment assessment.

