- d. Consent for recruiting and screening: Potential participants will be asked to contact the UW research team directly after learning about the study. 1) When a potential participant contacts the research team: A UW research staff will describe the study. If the potential participant is interested in participating in the study and determined to have decision making capacity, the research staff will ask if they are willing to voluntarily answer questions assessing eligibility over the phone and will be informed that they can refuse to answer any questions.

4. Study procedures:
 - a. A total of 30 individuals with early stage memory loss will be recruited from Washington, Oregon and California and randomly assigned to one of two groups: Personalized Care Network (n=15) or RMC (n=15).
 - b. Pre-treatment (baseline) assessment: The UW research staff will contact the 30 participants to schedule a pre-treatment assessment via telephone. They will complete

a 40-minute telephone assessment with either the study research coordinator or research study assistant.

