d. Participants in the **RMC group** will use the same routine medical care they are currently using as needed. Exercise and behavioral management training will not be provided to the RMC group. An online workshop will be offered to RMC participants after their post assessment. The workshop will focus on aging, memory loss and maximizing health and independence.

e. **Post-treatment assessments:** The UW research staff will conduct, via telephone, a post-treatment assessment after all sessions are completed to evaluate treatment effectiveness outcomes for participants. Participants will receive \$25 for each assessment.

5. Outcome Measure(s):

a. Change in Physical Activity [Time Frame: Baseline (pre-treatment) and 7 weeks (post-treatment)]

- Minutes spent on exercising per week in the past month were calculated from the following two questions: (1) How much time did you spend on exercises (hours per day) on a typical day during the last month; (2) How many days did you spend on exercises during the last month.

- b. Change in Physical Functioning [Time Frame: Baseline (pre-treatment) and 7 weeks (post-treatment)]
 - Physical functioning subscale of SF-36 (Medical Outcomes Study [MOS] 36-Item Short Form), consisting of 10 items assessing if participants' health limit them in activities such as walking, climbing, lifting, etc. on a 3-point scale ranging from 'yes, limited a lot' to 'no, not limited at all.'
- c. Change in Quality of Life [Time Frame: Baseline (pre-treatment) and 7 weeks (post-treatment)]
 - Quality of Life-AD scale assessed via interviews with participants, consisting of 13 items with a 4-point response scale (1 = poor to 4 = excellent) asking about their feeling about different aspects of life. Summary scores are a sum of the 13 items.

6. Identifiability of data

- a. Each and every subject will be assigned a unique identification number. This number serves as an indirect link between the assessment data collected and any identifying information gathered as a part of the study. Only the PIs and authorized research staff will have access to the link between data and the direct identifiers.
- b. Participants' name and their contact information (home address, email address, phone numbers) will be accessed by research staff to contact participants regarding the intervention and to schedule pre and post treatment assessments with participants.

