- a. Anticipated risks: Subjects in the study may be inconvenienced or experience psychological discomfort related to assessment questions including previous experiences of LGBT-specific adverse experiences and everyday discrimination. Subjects may also experience mild physical discomfort related to engaging in new physical exercise activities. These problems have not previously occurred in Drs. [name] or [name]'s studies, and we estimate the risks to be minimal. Subjects are informed that they are free to not answer any question and not to participate in any exercises.
- b. Protections against psychological discomfort: To minimize the risk of distress or emotional upset, the following steps will be taken: A) The PIs are experienced in conducting interviews and assessments by phone and in-person with subjects experiencing cognitive impairment and mood or behavioral disturbance; they are also experienced with research involving LGBT older adult health. Throughout the study they

will respond in a sensitive and respectful manner, in-person or by phone, to individuals who are distressed. B) The coaches will receive training from the PIs to monitor for distress and will be advised to immediately contact the PIs with any concerns related to the intervention or assessments resulting in psychological discomfort to the subjects. All concerns will be addressed in collaboration with the PIs. Subjects will be advised of their right to not answer any question(s) and/or to withdraw from the study at any time. No adverse emotional responses have been reported in our prior experience with training staff to deliver behavioral strategies. All sensitive questions in the proposed study are worded respectfully and have been used in previous studies with no adverse consequences. C) The coaches and assessment staff receive training on how to monitor for distress and how to identify and monitor potential triggers and redirect participants to other activities with more pleasant memories. D) If psychological distress is identified, for example severe depression or anxiety, referral to a primary care provider or mental health provider will be initiated. Resources (e.g. contact information of participants primary doctor or mental health provider) will be identified at the beginning of the intervention. Distress requiring referral has never occurred in previous studies of the intervention.

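### Two distress safeguards in section 9b, advance provider contacts and the instruction to alert the PIs, are tied to the intervention and the coaches and do not match the assessment calls where the named risk arises

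*Combined protocol and SAP*

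**What the plan says.** All references are to the combined protocol and SAP.

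- **Source of the risk (9a).** Subjects may "experience psychological discomfort related to assessment questions including previous experiences of LGBT-specific adverse experiences and everyday discrimination". The sentence is not limited to one arm or one time point.
- **Who is assessed, and when (3c, 4a).** Participants are "randomly assigned to one of two groups: Personalized Care Network (n=15) or RMC (n=15"), and "there are two assessments in total: a pre-treatment and a post-treatment assessment".
- **Who makes the calls (4b, 4e).** Baseline is "a 40-minute telephone assessment with either the study research coordinator or research study assistant". The post-treatment call is made by research staff, also by telephone, once the sessions are over.
- **What the RMC arm receives (4d).** "Exercise and behavioral management training will not be provided to the RMC group". These participants are offered an online workshop, but only after their post-treatment assessment.
- **Escalation (9b, item B).** "The coaches will receive training from the PIs to monitor for distress and will be advised to immediately contact the PIs with any concerns". The sentence goes on to cover concerns arising from the assessments as well as from the intervention.
- **Referral contacts (9b, item D).** "Resources (e.g. contact information of participants primary doctor or mental health provider) will be identified at the beginning of the intervention".

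**The concern.** The plan names a risk, places it in the assessment interview, and then sets up two of its protections at a different point in the study. Provider contacts are gathered when the intervention starts. Every baseline interview is over by then, and RMC participants never reach that point. The duty to alert the PIs immediately extends to concerns from assessments, yet it is given to the coaches, who are not the people section 4 puts on the assessment calls.

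What is at stake is readiness. If a participant becomes distressed on one of these calls, the caller may have to obtain a doctor's details from that person at that moment, and has no written instruction to alert the PIs at once. The study is aimed at people living with dementia who have no caregiver (objectives and background; this is the stated target population, not a listed inclusion criterion), so someone else in the home may not be there to help. The concern is participant protection. It does not touch the estimates or the tests.

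**Working it through.** The plan states no figure on this point, so there is none to reproduce. The check has two parts: set each safeguard against the calls, then count.

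**1. Does each safeguard, as worded, reach the assessment calls?**

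| Safeguard | Baseline calls, both arms | Post-treatment, intervention arm | Post-treatment, RMC |
|---|---|---|---|
| 9b(A) PIs respond to distressed individuals throughout the study | yes | yes | yes |
| 9b(B) right to decline questions or withdraw | yes | yes | yes |
| 9b(B) instruction to contact the PIs immediately | names coaches only | names coaches only | names coaches only |
| 9b(C) training to monitor for distress and redirect | yes, assessment staff named | yes | yes |
| 9b(D) referral if distress is identified | yes | yes | yes |
| 9b(D) provider contacts identified in advance | no | yes | no |
| 7c review of rights before each assessment | yes | yes | yes |

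Two rows fail. Item C names coaches and assessment staff as separate groups, and item B names only the first, so item B cannot simply be read as including both.

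**2. Is there another step that collects provider contacts?** None is described. The contact details listed in 6b are the participant's own. The consent visit (7a) has no such item.

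**3. Count of calls.** Inputs: 15 per arm (4a), 2 assessments each (3c).

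- Planned calls: 30 × 2 = 60.
- Before the intervention starts: 30 baseline calls, none with contacts in place.
- After treatment: 15 calls in the intervention arm with contacts, 15 in RMC without.
- Without contacts: 30 + 15 = 45, and 45/60 = 75%. With contacts: 15/60 = 25%.

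**4. Sensitivity.** The documents do not say whether the sensitive questions are asked at both assessments, and they give no dropout rate.

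- Sensitive questions at baseline only: 30 of 30 relevant calls lack contacts.
- At post-treatment only: 15 of 30.
- At both: 45 of 60.
- If a participants in the intervention arm and b in RMC miss the post-treatment call, the count without contacts is 45 − b out of 60 − a − b. All 30 baseline calls remain in it.

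Under each of these readings a substantial share of the relevant calls is missed.

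**The case against.** Most of section 9b does reach these calls. A reader might infer that the distress safeguards as a whole miss the RMC arm and the baseline interview. The table above shows otherwise: PI response, the right to decline, training of assessment staff, the referral rule and the review of rights all apply in both arms at both times. That objection stands and limits the point to two items.

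A reader might also infer that the plan could not carry out its own referral step. The text does not support this. Having contacts on file is not made a condition of referral, and they are given only as an example of resources. Participants are early stage and able to consent for themselves (7e), RMC participants keep their usual medical care (4d), and a caller can ask who the doctor is. Item B also says that all concerns are addressed together with the PIs.

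Third, the word intervention may be loose wording for study entry. Section 10 does describe both arms as intervention groups. However, 7c and item B each set the intervention and the assessments apart as different things, and section 4 puts baseline ahead of the intervention. The ambiguity is a reason to clarify and does not settle the matter.

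Last, the expected risk is low. Section 2c excludes people who are actively suicidal, hallucinating or delusional, or who had a recent psychiatric hospitalization. Section 9b reports that the sensitive questions were used before without adverse consequences, and that no distress needing referral arose in earlier studies of the intervention. This bears on urgency. It does not explain why a safeguard that the plan chose to include should be timed after half of the planned calls and left out of one arm.

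**Conclusion.** The point holds in a narrow form. As written, advance identification of provider contacts covers 15 of 60 planned assessment calls and misses 45 (75%), and the explicit instruction to alert the PIs immediately names only staff whom the plan does not assign to those calls. The count assumes full enrolment, no dropout, sensitive questions at both assessments, and a literal reading of when the intervention begins. The 45 are calls without contacts identified beforehand. They are not unprotected calls.

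A reader might go further and infer a bias between arms, because distress would be watched for more closely in the treated group. The documents give that no footing: distress and referral are not among the outcomes in section 5, and section 10 plans no comparison of them. The gap lies in preparation and in escalation wording. Sample size, analysis and interpretation of the outcomes are unaffected.

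**What to change.** Reconcile 9b(B) and 9b(D) with section 4, so that both the identification of contacts and the escalation instruction cover the assessment calls in both arms. One administrative way to do it:

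- in 9b(D), tie the identification of contacts to the consent visit (7a), for all participants;
- in 9b(B), name assessment staff alongside the coaches, as 9b(C) already does;
- in 6b, add provider contact details to the information that staff hold.

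If the sponsor meant something else by the beginning of the intervention, stating for each arm when contacts are identified would also resolve it. What counts as distress, and what the referral consists of, stay as they are.

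The cost is a few words in two items, one added contact item at a visit that already takes place, and the matching entry in 6b. No extra visit or call is needed.

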- e. Background: Lesbian, gay, bisexual, and transgender (LGBT) older adults are an at-risk, underserved, and rapidly growing population with elevated risk for Alzheimer's disease and related dementias (AD/RD). RDAD, which is grounded in social-learning and gerontological theories, is a present-focused cognitive-behavioral intervention aimed on increasing physical activity and problem-solving while engaging both members of caregiver (CG)-care recipient (CR) dyad. The focus of problem-solving in RDAD is specific to the needs of the CR and CG. RDAD, however, has not been translated to a highly stigmatized and marginalized population, such as LGBT older adults. Discrimination and stigma across the life course necessitate continual identity management for many LGBT older adults (e.g., nondisclosure), which may be complicated by cognitive decline in ways that increase stress. For example, with advanced memory decline the CR may inadvertently disclose to an intolerant family member or provider from whom they had previously concealed their identity, resulting in conflict or interpersonal discomfort that the CG must manage and negotiate. Thus, it is essential to address the unique characteristics in RDAD to improve treatment effects. In addition to these unique situations, LGBT older adults are significantly less likely to be

married or to have biological family members, and a significant proportion of LGBT older adults living with AD/RD has no caregiver or care network. This study adds a modification to RDAD that will deliver the intervention to LGBT older adults with AD/RD who do not have caregivers. Building off of the study that is to extend and test the RDAD intervention with a growing underserved and stigmatized population (IRB STUDY00003076), this study pilot-tests feasibility and efficacy of Aging with Pride: Innovations in Dementia Empowerment and Action (IDEA), a modified version of RDAD tailored to better respond to distinct risks, particularly among LGBT older adults living with AD/RD without a caregiver. In this pilot study the modified version of RDAD intervention is referred to the Personalized Care Network.

2. Participants

- a. General characteristics: 30 LGBT individuals with AD/RD aged 50 or older will participate in the study.

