c. **Interventions:** For the **Personalized Care Network group**, the intervention will be done virtually using a video conferencing platform such as Zoom. Two coaches will meet with 4-6 individuals for 9 one-hour sessions over six weeks. We will use the treatment manual developed and used for an earlier translational research (IRB STUDY00003076, Title: Older Adults Living with Alzheimer's Disease and their Caregivers, PI: [name]). The manual was modified in March 2020 in order to transition from an in-home intervention to a virtual intervention. The manual includes text for the coaches, graphic illustrations of exercises, handouts, and process/treatment fidelity forms. A video link demonstrating exercises will be provided to participants. The coaches will encourage and help participants with their exercises, and develop plans to address difficult behaviors. The exercise component includes seated exercises with aerobic/endurance activities, strength training, and exercises to improve balance and flexibility. Exercises are introduced incrementally and individualized to meet the needs of each person. Each exercise is first demonstrated by the coach, then practiced by the participants. Coaches monitor the exercises closely in order to ensure that they are practiced safely and correctly. In the behavior management component, the ABC technique is applied. Study participants are taught to identify the antecedent (A) to a behavioral issue or problem (B) as well as the consequences (C) of the behavior. Participants are instructed to identify and modify behavioral problems that can impair day-to-day function and interfere with exercise participation. They are given specific training in how to identify precipitants of problem behaviors, and how to modulate their own responses to these problems. Participants are also encouraged to identify pleasant activities that can be incorporated into the exercise program. An Exercise Coach will meet via a video conferencing platform individually with each treatment group participant once a week for 6 weeks to ensure exercises are done safely and correctly. Participants in the treatment group will be invited to participate in a focus group after their post treatment assessment is completed.

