- c. Protections against physical discomfort: If subjects experience mild physical discomfort related to engaging in new physical exercise activities, they will be informed that they do not need to participate in any exercises. We estimate physical discomfort to be minimal in the proposed study.
- d. A potential breach of confidentiality regarding subjects' sexual/gender identity and/or medical condition may cause psychological or social harm. All team members have signed a confidentiality agreement prior to being involved in the study. All participant information is to be kept strictly confidential with the only exception being incidents of abuse of a dependent adult or minor child and risks of imminent harm to others or to the subject. All researchers have completed training in research with human subjects.

10. Analysis plan

- a. The point estimates of the proportions of eligible participants who agree to participate in the study and enrolled participants who comply with exercise assignments and adhere to the program sessions will be computed to test enrollment feasibility and intervention acceptability. Data from all measures at each time point will be examined utilizing univariate statistics in which psychometric properties of each variable will be determined. While random assignment is expected to produce comparable intervention groups, this will be ensured by comparing demographic characteristics and outcomes of interest at the baseline across intervention groups. To test initial efficacy of the Personalized Care Network approach and RMC on primary outcomes, we will use ANCOVA, which helps to reduce error variance, yielding a more powerful test. The proposed sample size is sufficient to detect a medium effect of the preliminary intervention,⁸ which is greater than a clinically important difference level.⁹ We will compute and assess confidence intervals to evaluate precision of sample estimates and effect sizes for each outcome variable so as to derive proper sample size for the next stage of the study.

References

1. [name] KI, Kim H-J, Barkan SE, Muraco A, Hoy-Ellis CP. Health disparities among lesbian, gay, and bisexual older adults: Results from a population-based study. *American Journal of Public Health*. 2013;103(10):1802-1809.

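### The plan specifies no recording, reporting route or analysis of falls, injuries or unplanned medical care in either arm of a remote exercise pilot for people with dementia and no caregiver

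*Combined protocol and SAP*

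**What the plan says.** Section 4c describes the treated arm's programme: "The exercise component includes seated exercises with aerobic/endurance activities, strength training, and exercises to improve balance and flexibility". Delivery is remote: "the intervention will be done virtually using a video conferencing platform such as Zoom". There are nine group sessions over six weeks, and an Exercise Coach also meets each treated participant individually once a week for six weeks. Item e (Background) gives the purpose of the modification, which is to "deliver the intervention to LGBT older adults with AD/RD who do not have caregivers".

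On risk, section 9a names mild physical discomfort, says such problems did not arise in the investigators' previous studies, and concludes "we estimate the risks to be minimal". Section 9c's protection is that a participant with discomfort is told the exercises are optional. It ends: "We estimate physical discomfort to be minimal in the proposed study". Section 9b tells coaches to contact the investigators at once about concerns that cause psychological discomfort. No matching route is given for a physical event.

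Section 5 lists three outcomes, each at baseline and 7 weeks: exercise minutes, SF-36 physical functioning and QoL-AD. Section 4e describes the post-treatment call as an effectiveness assessment. Section 10a covers enrolment, compliance and adherence, baseline comparability, ANCOVA on the primary outcomes, and interval estimates for planning the next study. Neither the outcomes nor the analysis plan has an item on falls, injuries or unplanned care.

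**The concern.** The pilot takes an exercise programme with strength and balance components to people with early-stage dementia who have no caregiver, with the coach on a screen. Items c and e describe the parent programme as training a caregiver and care recipient together. A caregiver is someone who might notice and report a fall or injury. Here that observer is missing, and participants with memory loss may not volunteer an event.

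The plan relies on past experience for its risk estimate and provides no means of checking it in this setting. The study could therefore end with adherence and effect-size estimates for planning the next stage and no usable account of harms. It might instead have a few unsolicited reports gathered under very different contact in the two arms, which could not be fairly compared.

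**Working it through.** The plan gives no safety figure to reproduce, so the main check is a reading of the sections, followed by arithmetic on what 15 per arm could show.

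**Protection set against data capture**

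| Provision | Section | Protects? | Records events? |
|---|---|---|---|
| Seated format, incremental and individualised exercises | 4c | Yes | No |
| Exclusion of people whose physical conditions prevent exercise | 2c | Yes | No |
| Live supervision and weekly Exercise Coach meeting | 4c | Yes, treated arm | None stated |
| Process/treatment fidelity forms | 4c | – | None stated; content not shown |
| Escalation to investigators | 9b | Yes | Psychological concerns only; no data record stated |
| Freedom to skip exercises | 9a, 9c | Yes | No |
| Outcomes at baseline and 7 weeks | 5 | – | No event item |
| Analysis | 10a | – | No event table |

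SF-36 physical functioning might fall after an injury, but it cannot identify or count one.

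**Contact by arm.** Between the two assessments the treated arm has 9 group sessions + 6 individual meetings = 15 scheduled contacts. None is described for the control arm, whose workshop follows the post-treatment assessment (section 4d). Opportunities to report spontaneously are therefore very unequal.

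**Exposure outside supervision.** Section 10a counts compliance with exercise assignments, section 4c supplies a demonstration video, and the first outcome is exercise minutes per week. I infer that some exercise takes place with no coach watching.

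**Chance that events occur.** Input: n = 15 per arm (sections 2d and 4a). The documents give no fall risk, so the 7-week risk p is assumed. P(at least one) = 1 − (1 − p)^15.

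- p = 2%: 1 − 0.98^15 = 26%
- p = 5%: 1 − 0.95^15 = 54%
- p = 10%: 1 − 0.90^15 = 79%
- p = 20%: 1 − 0.80^15 = 96%

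**What zero events would show.** The one-sided 95% upper bound is 1 − 0.05^(1/n).

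- n = 15: 1 − 0.05^(1/15) = 18.1% (upper limit of the two-sided 95% interval: 1 − 0.025^(1/15) = 21.8%)
- n = 30, arms pooled: 1 − 0.05^(1/30) = 9.5% (two-sided: 11.6%)

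**What a comparison would show.** For 0 of 15 against 4 of 15, the two-sided Fisher exact p = 2 × C(15,4)/C(30,4) = 2 × 1,365/27,405 = 0.10. Even that split would not reach the 5% level, so a between-arm comparison can only be descriptive.

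**The case against.** The strongest reply is that the documents are silent, which is not the same as excluding collection. The questionnaires are not reproduced. The 40-minute assessment is evidently wider than the three outcomes, since section 9a refers to questions on adverse LGBT-specific experiences and discrimination. A reader might infer that falls and injuries are definitely not asked about and that safety cannot be assessed at all. The text does not support that; it supports only that no collection is specified.

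Second, the plan takes real precautions: seated exercise, early-stage participants, physical exclusions and close supervision. These lower the likely risk and bear on how serious the gap is, but they leave it open.

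Third, a reader might infer that reports could come only from treated participants. Controls also have the 7-week call, and assessment staff are trained to watch for distress, so mainly is the defensible word.

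Fourth, it is tempting to treat virtual delivery as wholly untested. The plan says "The manual was modified in March 2020 in order to transition from an in-home intervention to a virtual intervention", but not whether the parent study then ran virtually, or that all the studies behind the risk statement were in-home. The missing caregiver is the better-supported difference, although it comes from items c and e and is not among the listed criteria in section 2b.

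Fifth, the 18% bound does not refute the closing sentence of section 9c, which concerns discomfort and not falls. Nor could full collection in 15 people establish that fall risk is minimal.

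Finally, Aim 2 names acceptability, feasibility and initial efficacy, and no go/no-go rule is stated. That planning the next stage should draw on harms data is a judgement, though an ordinary one for an exercise pilot.

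**Conclusion.** The gap is real and should be closed. Neither arm has a specified record, reporting route or analysis for falls, injuries or unplanned medical care, and a team following the text would have no systematic or comparable harms data from a caregiver-free remote exercise programme. The safeguards do not substitute for this, and the stated escalation route omits physical events.

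The likelihood of there being something to record depends on an assumed risk: 26% to 96% for at least one affected person among 15, for 7-week risks of 2% to 20%. These figures assume that all 15 are followed and that participants are independent. Counts would be coarse, since zero of 15 excludes only risks above about 18% (one-sided 95%). They would still give a description, which the present text does not provide for. The conclusion rests on the protocol text; if the unseen questionnaires or fidelity forms already contain event questions, what remains is to state them, add the reporting route and plan the table.

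**What to change.** - **Section 4e, both arms:** ask the same short scripted questions at the existing 7-week call about falls, injuries and unplanned medical care since baseline.
- **Section 4c, treated arm:** add a brief check to each weekly Exercise Coach meeting for safety monitoring. List these reports separately and keep them out of the between-arm table.
- **Section 9:** have physical events passed to the investigators as psychological concerns already are. How an event is managed stays with the investigators.
- **Section 10a:** add a descriptive table, from the 7-week answers, of participants with an event and number of events by arm. Give exact confidence intervals for the participant proportions and no hypothesis test. Note beside it that zero of 15 leaves a one-sided 95% upper bound of 18%. Note also that weekly prompting of one arm and seven-week recall by people with memory loss may make ascertainment unequal.

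The cost is a few questions in contacts that already take place, slightly longer calls and one table. The counts will be imprecise and self-reported, and the weekly check may itself improve recall in the treated arm. Reporting the weekly listing apart from the 7-week answers makes that visible but does not remove it.
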